**Table 8-1 Assessment Schedule**

Period	Screening	Baseline	Double-Blind Treatment Period 			Safety Follow-up
Visit Name	Screening 	V1	V2 	V3	V4 	V5 (EOS) 
Days	-14 to -1	1	30	90	150	180 +5
Informed consent	X					
Inclusion / Exclusion criteria	X	X				
Demography	X					
Smoking and alcohol history	X					
Medical history/current medical conditions	X					
Prior or concomitant medication 	X	X	X	X	X	X
Surgical/medical procedures 	X	X	X	X	X	X
Physical Examination	S	S		S		S
Body Height/Weight	X					
Vital Signs 	X	X	X	X	X	X
AEs/SAEs	X	X	X	X	X	X
Lifestyle instructions		S	S	S	S	S
Electrocardiogram (ECG)		X				
Follicle stimulating hormone (FSH)	X 					

Period	Screening	Baseline	Double-Blind Treatment Period 			Safety Follow-up
Visit Name	Screening 	V1	V2 	V3	V4 	V5 (EOS) 
Days	-14 to -1	1	30	90	150	180 +5
Pregnancy Test (serum) 	X					
Pregnancy Test (urine) 		X	X	X	X	X
Thyroid stimulating hormone 	X					
Fasting Lipid Profile 	X	X	X	X	X	
Fasting Lp(a) 		X			X	
PCSK9 		X	X	X	X	
Clinical Chemistry 	X					
Limited Chemistry 		X	X		X	X
Hematology 		X				X
HbA1c 	X					X
Urinalysis 	X					X
Coagulation Panel 		X				
Enter participant visit in IRT	X	X	X	X	X	X
Randomization		X				
Study drug administration - s.c. inclisiran/placebo		X 		X 		
Dispense ezetimibe/placebo		S	S	S		

Period	Screening	Baseline	Double-Blind Treatment Period 			Safety Follow-up
Visit Name	Screening 	V1	V2 	V3	V4 	V5 (EOS) 
Days	-14 to -1	1	30	90	150	180 +5
Control drug administration - p.o. ezetimibe/placebo		X 	X 	X 	X 	
Ezetimibe/placebo compliance			X 	X 	X 	
Disposition form	X				X 	X

 Assessment to be recorded in the clinical database or received electronically from a vendor

 Visit may be performed off-site in certain countries and sites as determined by protocol needs and based on national and local/site regulations.

 Visit 4 is also the EOT visit if the participant completes the study treatment as per protocol.

 Visit may be performed off-site in certain countries and sites as determined by protocol needs and based on national and local/site regulations or over the telephone if an on-site visit is not possible. During a telephone call, only AEs/SAEs and concomitant medications will be followed.

 When study treatment is discontinued early, participants should continue with all of their planned study visits and be retained until Day 180. A window of +/- 5 days based on the Day 1 visit date is acceptable for Visit 2 (Day 30), Visit 3 (Day 90), and Visit 4 (Day 150).

 All medications, procedures, and significant non-drug therapies used by/Performed on the participant within 30 days prior to the first visit (Screening visit) and throughout the study must be documented in the appropriate page of the eCRF.

 Blood pressure and pulse will be taken 3 times in sitting position.

 Required for any female participant who is considered as surgically sterile or post-menopausal in the absence of medical documentation confirming this reproductive/menopausal status at screening (see [Section 8.4.3](#)).

 Only in women of childbearing potential (see [Section 5.2 - Exclusion Criterion #14](#) and [Section 8.4.3](#)). Serum samples will be sent to the central lab for analysis.

 Only in women of childbearing potential (see [Section 5.2- Exclusion Criterion #14](#) and [Section 8.4.3](#)). Performed locally, using central laboratory kit supplies. If urine test is positive, a serum sample will be sent to the central lab for analysis.

 Performed by the central lab. See [Table 8-3](#).

 Performed by the central lab. Includes LDL-C, Apo A-1, Apo B, Apo B/Apo A-1 ratio, non-HDL-C, TC, HDL-C, TC/HDL-C ratio, triglycerides.

 Performed by the central lab. An additional aliquot will be made from the PCSK9 sample in order to allow analysis of proteins related to dyslipidemia or study drug mechanism.

 Performed locally, using central laboratory kit supplies. If Macroscopic Panel (Dipstick) results are positive (abnormal) for Leukocyte Esterase, Nitrite, Blood, and/or Protein, then a urine sample will be sent to central lab to perform a Macroscopic Panel and a Microscopic Reflexive Panel if positive for Leukocyte Esterase, Nitrite, Blood, Protein. Refer to [Table 8-3](#).

 Subcutaneous inclisiran/placebo will be administered by qualified healthcare personnel after all other study assessments have been completed for this visit.

Period	Screening	Baseline	Double-Blind Treatment Period 			Safety Follow-up
Visit Name	Screening 	V1	V2 	V3	V4 	V5 (EOS) 
Days	-14 to -1	1	30	90	150	180 +5

16 Participant to take one capsule ezetimibe/placebo a day starting from Day 1 until the day before the Day 150 visit (see [Section 6.3.2](#)).

Compliance will be checked until the visit following the last dose of ezetimibe/placebo.

17 End of Treatment disposition form should be completed prior to Day 150 if the participant discontinues study treatment prior to Day 150.

## 8.1 Screening

### Screening

Screening activities must be initiated only after the ICF has been signed.

If a safety laboratory assessment during the screening period is outside of the range specified in the exclusion criteria, the assessment may be repeated one time prior to randomization. If the repeat value remains outside of the specified ranges, the participant will be considered a screen fail and must be excluded from the study.

It is generally not permissible to re-screen a participant if he/she fails the initial screening. Re-screening is allowed once, if a participant has an initiation, a dose change or a discontinuation of medications that are known to induce lipid and lipoprotein changes (see [Section 5.2 - Exclusion Criterion #3](#)) within 30 days prior to screening or post screening but before randomization. Participants may be re-screened after being on a stable dose for 30 days or after treatment discontinuation of such medications for 30 days.

Re-screened participants must provide new written informed consent. A new participant number will be assigned to the re-screened participants and the site must record the re-screening information in the corresponding eCRF and in IRT. All screening procedures will need to be re-performed.

#### 8.1.1 Information to be collected on screening failures

Participants who sign the ICF and are subsequently found to be ineligible at time of randomization will be considered a screen failure. The reason for screen failure should be recorded on the appropriate eCRF page. The demographic information, informed consent, and inclusion/exclusion eCRF pages must be completed for screen failure participants. No other data are required to be entered into the clinical database for participants who are screen failures, unless the participant experienced a SAE during the screening period (see [Section 10.1.3](#) for reporting details). If the participant fails to be randomized, the IRT must be notified within 2 days of the screen fail.

Participants who are randomized and fail to start treatment (e.g., participants randomized in error) will be considered an early terminator. The reason for early termination should be recorded in the appropriate eCRF page.

## 8.2 Participant demographics/other baseline characteristics

Country-specific regulations should be considered for the collection of demographic and baseline characteristics in alignment with the eCRF.

Participant demographic and baseline characteristics collected on all participants include: age, sex, race, ethnicity, vital signs, height, weight, smoking/alcohol history, medical history/current medical conditions present before signing the ICF (where possible, diagnoses and not symptoms should be recorded), and relevant laboratory tests.

Participant race/ethnicity data are collected and analyzed to identify any differences in safety and/or efficacy due to these factors, as well as to assess the diversity of the study population as required by Health Authorities.

All prescription and over-the-counter medications, procedures, and significant non-drug therapies, used by/performed on the participant within 30 days prior to the first visit (Screening visit) and throughout the study must be documented in the appropriate page of the eCRF (see [Section 6.2.1](#)).

Investigators will have the discretion to record abnormal test findings on the medical history eCRF whenever, in their judgment, the test abnormality occurred prior to the informed consent signature.

## **8.3 Efficacy**

All efficacy assessments are biomarkers which will be analyzed at a central laboratory. Specimens for efficacy assessments will be collected at time points specified in the Assessment Schedule ([Table 8-1](#)). Participants must be in a fasted state for all of these laboratory assessments. Details regarding the collection, processing, shipping and storage of the samples for central laboratory will be provided in a Laboratory Manual.

Starting from the time of the randomization visit (Day 1), the results from all lipid parameter measurements must be blinded to participants, investigator staff, persons performing the assessments, the monitors, and the Novartis Clinical Trial Team (CTT) until database lock.

### **8.3.1 LDL-C**

The primary efficacy assessment will be LDL-C, as tested and reported by the central laboratory as part of the Lipid Panel at the frequency shown in [Table 8-1](#). Participants must be fasting for all LDL-C assessments.

### **8.3.2 Additional efficacy assessments**

Additional efficacy assessments will include non-HDL-C, HDL-C, TC, TC/HDL-C ratio, Apo A-1, Apo B, Apo B/Apo A-1 ratio, Lipoprotein A (Lp(a), and PCSK9. Lipid parameters, Lp(a) and PCSK9 will be tested and reported by the central laboratory at the frequency shown in [Table 8-1](#). Participants must be fasting for all lipid and lipoprotein testing.

### **8.3.3 Appropriateness of efficacy assessments**

Inclisiran is a siRNA which acts to inhibit the synthesis of PCSK9 protein, which consequently reduces LDL-C in circulation. LDL-C is a well-defined and validated laboratory parameter and is routinely assessed in clinical trials. LDL-C reduction is an accepted surrogate for CV risk reduction, e.g., for statins and PCSK9- blocking monoclonal antibodies. While multiple factors contributing to the development of ASCVD have been described, strong and consistent evidence from genetics, epidemiology, Mendelian randomization studies, and randomized trials have established that LDL-C is not only a laboratory parameter of increased risk, but also a causal and modifiable factor in ASCVD ([Mach et al 2020](#)). Laboratory tests related to the primary and secondary endpoints are in line with the expected efficacy of inclisiran.

## 8.4 Safety

Safety assessments are specified below, with the Assessment Schedule ([Table 8-1](#)) detailing when each assessment is performed.

For details on AE collection and reporting, refer to AE section ([Section 10.1](#)).

As per [Section 4.7](#), during a Public Health emergency as declared by Local or Regional authorities i.e. pandemic, epidemic or natural disaster, that limits or prevents on-site study visits, regular phone or virtual calls can occur (every 4 weeks or more frequently if needed) for safety monitoring and discussion of the participant's health status until it is safe for the participant to visit the site again.

**Table 8-2 Safety assessments**

Assessment	Specification
Physical examination	
A complete physical examination will include the examination of general appearance, skin, neck (including thyroid), eyes, ears, nose, throat, lungs, heart, abdomen, back, lymph nodes, extremities, vascular, and neurological. If indicated based on medical history and/or symptoms, rectal, external genitalia, breast, and pelvic exams will be performed.
 
Information for all physical examinations must be included in the source documentation at the study site. Clinically relevant findings that are present prior to signing informed consent must be recorded on the appropriate eCRF that captures medical history. Significant findings made after signing informed consent which meet the definition of an AE must be recorded as an AE.

Vital signs	
Vital signs include blood pressure (BP) and pulse measurements. After the participant has been sitting for five minutes, with back supported and both feet placed on the floor, systolic and diastolic blood pressure and pulse will be measured three times using an automated validated device with an appropriately sized cuff. The repeat sitting measurements will be made at 1 - 2 minute intervals and the mean of the three measurements will be used. In case the cuff sizes available are not large enough for the participant's arm circumference, a sphygmomanometer with an appropriately sized cuff may be used.

Height and weight	Height in centimeters (cm) and body weight (to the nearest 0.1 kilogram (kg) in indoor clothing, but without shoes) will be measured.

### 8.4.1 Laboratory evaluations

Specimens will be obtained at the time points detailed in the Assessment Schedule ([Table 8-1](#)). Details on what is included in chemistry (full and limited panels), hematology, coagulation, thyroid stimulating hormone, and urinalysis laboratory evaluations as well as pregnancy testing and FSH are provided in [Table 8-3](#).

The central laboratory will flag laboratory values falling outside of the normal ranges on the central laboratory reports. Investigators are responsible for reviewing these abnormal values for clinical significance, signing the laboratory reports to indicate their review, and reporting values considered clinically significant in the appropriate eCRF. Any clinically significant abnormal laboratory value should be evaluated and followed-up by the investigator until normal or a cause for the abnormality is determined. Clinically significant abnormalities must be recorded as either medical history/current medical conditions or AEs as appropriate.

In addition to [Table 8-3](#), see [Section 6.6.3.1](#) for follow-up on potential DILI cases, [Section 10.2.1](#) for liver safety monitoring, and [Section 16.2](#) for specific liver event and

laboratory test trigger definitions and follow-up requirements and [Section 10.2.2](#) for renal safety monitoring.

Central laboratory will be used for analysis of all specimens collected, with the exception of urine pregnancy tests and manual dipstick urinalysis, which will be done locally (using testing materials supplied by the central laboratory). Serum pregnancy tests at screening will be done by the central laboratory. Details on the collections, shipment of samples and reporting of results by the central laboratory are provided to investigators in a Laboratory Manual.

As per [Section 4.7](#), during a Public Health emergency as declared by Local or Regional authorities, i.e. pandemic, epidemic or natural disaster, that limits or prevents on-site study visits, if participants cannot visit the site for protocol specified safety lab assessments, an alternative lab (local) collection site may be used.

**Table 8-3 Safety Laboratory Assessments**

Test Category	Test Name
Hematology	Hematocrit, Hemoglobin, Mean Corpuscular Hemoglobin (MCH), Mean Corpuscular Hemoglobin Concentration (MCHC), MCV, Platelets, Erythrocytes, Leukocytes, Differential (% of Basophils, Eosinophils, Lymphocytes, Monocytes, Neutrophils)
HbA1c	HbA1c
Chemistry (full panel)	AST, ALT, ALP, GGT, TBL, Direct Bilirubin, Indirect Bilirubin, Albumin, Creatinine, eGFR, Blood Urea Nitrogen (BUN), Uric Acid, Fasting Plasma Glucose (FPG), CK, Calcium, Magnesium, Phosphate, Chloride, Sodium, Potassium
Chemistry (limited panel)	AST, ALT, ALP, GGT, TBL, Creatinine, eGFR, FPG, CK
Urinalysis	Macroscopic Panel (Dipstick): Color, Bilirubin, Occult Blood, Macroscopic Blood, Glucose, Ketones, Leukocyte esterase, Nitrite, pH, Protein, Specific Gravity, Urobilinogen. If dipstick results are positive (abnormal) for Leukocyte Esterase, Nitrite, Blood, and/or Protein, then a urine sample will be sent to the central lab to perform a Macroscopic Panel and a Microscopic Reflexive Panel if there are positive results for Leukocyte Esterase, Nitrite, Blood, and/or Protein. Microscopic Panel: Erythrocytes, Leukocytes, Casts, Crystals, Bacteria, Epithelial cells.
Coagulation	PT, INR, Activated partial thromboplastin time (APTT)
Thyroid Function	Thyroid Stimulating Hormone
Pregnancy Test	Serum and Urine Pregnancy (see Section 8.4.3 ) A confirmatory serum pregnancy test is required in case of a positive urine pregnancy test.
Follicle Stimulating Hormone	FSH (see Section 8.4.3 ) Required for any female participant considered surgically sterile or post-menopausal in the absence of medical documentation confirming this reproductive/menopausal status at screening.
Liver Event Testing and Liver Follow-up Testing	Albumin, ALP, ALT, AST, CK, GGT, GLDH, INR, PT, and Total Bilirubin (TBL). Test for hemolysis (haptoglobin, reticulocytes, unconjugated [indirect] bilirubin). These tests are in addition to routine testing, to be performed only in follow-up to safety events when indicated in Section 6.6.3.1 , Section 10.2.1 and Section 16.2 .
Renal Follow-up	Urine protein for Protein:Creatinine ratio (PCR), Serum Creatinine. Repeat standard urinalysis. Macroscopic Panel (Dipstick) Color, Bilirubin, Occult Blood, Macroscopic Blood, Glucose, Ketones, Leukocyte esterase, Nitrite, pH, Protein, Specific Gravity, Urobilinogen. If dipstick results are positive (abnormal), for Leukocyte Esterase, Nitrite, Blood and/or Protein, then a urine sample will be sent to the central lab to perform a Macroscopic Macroscopic Panel and a Microscopic Reflexive Panel if there are positive results for

Test Category	Test Name
	Leukocyte Esterase, Nitrite, Blood, and/or Protein. Microscopic Panel: Erythrocytes, Leukocytes, Casts, Crystals, Bacteria, Epithelial cells. These tests are in addition to routine testing, to be performed only in follow-up to safety events when indicated in Section 10.2.2 .

#### 8.4.2    **Electrocardiogram (ECG)**

Single 12 lead ECGs will be conducted using local ECG machines. ECGs must be recorded after 10 minutes rest in the supine position to ensure a stable baseline. The preferred sequence of cardiovascular data collection during study visits is ECG collection first, followed by vital signs, and blood sampling.

ECGs will be locally collected and evaluated. Interpretation of the baseline tracing must be made by a qualified physician and documented on the ECG CRF. Each ECG tracing should be labeled with the study number, participant initials (where regulations permit), participant number, date, and kept in the source documents at the study site.

The QT interval corrected by Fridericia's formula (QTcF) should be used for clinical decisions. The investigator must calculate QTcF if it is not auto-calculated by the ECG machine. Clinically significant abnormalities at baseline should be reported on the adverse events eCRF.

Clinically significant findings must be discussed with Novartis prior to enrolling the participant in the study.

Additional, unscheduled, safety ECGs may be repeated at the discretion of the investigator at any time during the study as clinically indicated. For any ECGs with participant safety concerns, two additional ECGs must be performed to confirm the safety finding. ECG safety monitoring, or a review process, should be in place for clinically significant ECG findings at baseline before administration of study treatment and during the study.

New or worsened clinically significant findings occurring after informed consent must be recorded as adverse events. The original ECGs on non-heat-sensitive paper and a certified copy on non-heat sensitive paper, appropriately signed, must be collected and archived at the study site.

#### 8.4.3    **Pregnancy and assessments of fertility**

All pre-menopausal women who are not surgically sterile will have a serum pregnancy test performed at the screening visit, and urine pregnancy tests at all other study visits. If a urine pregnancy test is positive, then a serum pregnancy test will be performed.

Additional pregnancy testing might be performed if requested by local requirements.

If participants cannot visit the site to have serum pregnancy tests during a Public Health emergency as declared by Local or Regional authorities, i.e., pandemic, epidemic or natural disaster, that limits or prevents on-site study visits, urine pregnancy test kits may be used. Relevant participants can perform the urine pregnancy test at home and report the result to the site. It is important that participants are instructed to perform the urine pregnancy test first and only if the test result is negative proceed with the administration of the study treatment. A communication process should be established with the participant so that the Site is informed and can verify the pregnancy test results (e.g., following country specific measures).

## **Assessments of fertility**

Medical documentation of oophorectomy, hysterectomy, or tubal ligation must be retained as source documents. Subsequent hormone level assessment to confirm the woman is not of childbearing potential must also be available as source documentation in the following case:

- Surgical bilateral oophorectomy without a hysterectomy.

In the absence of the above medical documentation (confirming that participant is either surgically sterile or post-menopausal, see [Section 5.2](#) - Exclusion Criterion #14 for additional information), FSH testing is required of any female participant regardless of reported reproductive/menopausal status at screening.

### **8.4.4 Appropriateness of safety measurements**

The safety assessments selected are standard for this indication/participant population.

## **8.5 Additional assessments**

### **8.5.1 Trial Feedback Questionnaire**

By participating in the clinical trial, participants may be contacted for feedback about their trial experience, as appropriate and in adherence to local regulations and guidelines. Responses may be used by Novartis to understand where improvements can be made in the clinical trial process. The feedback asks questions about trial experience. It does not ask questions about the trial participant's disease, symptoms, treatment effect, or AEs, and, therefore is not considered as trial data.

### **8.5.3 Lifestyle instructions**

Investigators will instruct their participants from the randomization visit through the Day 180 visit that the most important way to prevent ASCVD is to promote a healthy lifestyle throughout life. Prevention strategies must include a strong focus on lifestyle optimization (improvements in diet, physical activity, and avoidance of tobacco use and exposure to secondhand smoke) to minimize the risk of future ASCVD events (Arnett et al 2019).

## 9 Discontinuation and completion

### 9.1 Discontinuation from study treatment and from study

#### 9.1.1 Discontinuation from study treatment

Discontinuation of study treatment for a participant occurs when study treatment is permanently stopped for any reason (prior to the planned completion of study drug or control drug administration, if any) and can be initiated by either the participant or the investigator. If the participant permanently discontinues p.o. ezetimibe/placebo or s.c. inclisiran/placebo, then the participant's entire study treatment must be stopped. The treatment disposition CRF will be completed to reflect that the participant has permanently discontinued study treatment (both p.o. study drug and s.c. study drug).

The investigator must discontinue study treatment for a given participant if he/she believes that continuation would negatively impact the participant's well-being.

Discontinuation from study treatment is required under the following circumstances:

- Participant/guardian decision
- Pregnancy
- Use of prohibited treatment as per recommendations in the prohibited medication [Section 6.2.2](#)
- Any situation in which continued study participation might result in a safety risk to the participant
- Severe and persistent (> 14 days despite appropriate treatment) reactions at the injection site and any type of anaphylactic reactions
- Intolerable adverse events
- Unexplained increases in transaminases (ALT or AST) or total bilirubin confirmed by repeat test as follows:
  - ALT or AST > 8 x ULN
  - ALT or AST > 5 x ULN for more than 2 weeks
  - ALT or AST > 3 x ULN with simultaneous or subsequent elevation of total bilirubin > 2 x ULN
  - ALT or AST > 3 x ULN with the appearance of fatigue, nausea, vomiting, right upper quadrant pain or tenderness, fever, rash, and/or eosinophilia (> 5%)

The investigator should evaluate to see if other causes for the laboratory abnormalities are immediately apparent, such as obstructive gall bladder or bile duct disease, viral or alcoholic hepatitis, malignancy involving the liver, congestive hepatopathy, other hepatotoxins or heritable disorders. Please also refer to [Section 16.2 Appendix 2](#).

- Unexplained CK > 10 x ULN confirmed by repeat test when the CK elevation is associated with muscle pain, muscle tenderness and/or muscle weakness, or new onset renal dysfunction with no other alternative explanation
- Following emergency unblinding

- Any other laboratory abnormalities that in the judgment of the investigator, taking into consideration the participant's overall status, prevents the participant from continuing participation in the study

If discontinuation from study treatment occurs, the investigator should make a reasonable effort to understand the primary reason for the participant's discontinuation from study treatment and record this information.

Participants who discontinue from study treatment should continue with planned study visits and be retained until Day 180 as indicated in the Assessment Schedule. Refer to [Table 8-1](#) Assessment Schedule.

If the participant cannot or is unwilling to attend any visit(s), the site staff should maintain regular telephone contact with the participant, or with a person pre-designated by the participant. This telephone contact should preferably be done according to the study visit schedule.

After discontinuation from study treatment, at a minimum, in abbreviated visits, the following data should be collected at clinic visits or via telephone/email contact:

- New / concomitant treatments
- AEs / SAEs

The investigator must also contact the IRT to register the participant's discontinuation from study treatment.

If discontinuation occurs because treatment code has been broken, please refer to Emergency breaking of treatment code section.

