## **10.2 Additional Safety Monitoring**

### **10.2.1 Liver safety monitoring**

To ensure participant safety and enhance reliability in determining the hepatotoxic potential of an investigational drug, a standardized process for identification, monitoring and evaluation of liver events has to be followed.

Please refer to [Table 16-1](#) in [Section 16.2](#) for complete definitions of liver laboratory triggers.

Once a participant is exposed to study treatment, every liver event defined in [Table 16-1](#) should be followed up by the investigator or designated personnel at the trial site, as summarized below. Additional details on actions required in case of liver events are outlined in [Table 16-2](#) and [Table 16-3 \(Section 16.2\)](#). Repeat liver chemistry tests (i.e., ALT, AST, TBL, albumin, CK, GLDH, PT/INR, ALP and GGT) to confirm elevation. These liver chemistry repeats will be performed using the central laboratory. If results will not be available from the central laboratory, then the repeats can also be performed at a local laboratory to monitor the safety of the participant. If a liver event is subsequently reported, any local liver chemistry tests previously conducted that are associated with this event should have results recorded on the appropriate eCRF.

- If the initial elevation is confirmed, close observation of the participant will be initiated, including consideration of treatment interruption if deemed appropriate.
- Discontinuation of the investigational drug (refer to the Discontinuation of study treatment section), if appropriate
- Hospitalization of the participant if appropriate
- Causality assessment of the liver event
- Thorough follow-up of the liver event should include (based on investigator's discretion): serology tests, imaging and pathology assessments, hepatologist's consultancy; obtaining more detailed history of symptoms and prior or concurrent diseases, history of concomitant drug use, exclusion of underlying liver disease

All follow-up information and procedures performed must be recorded as appropriate in the eCRF.

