**Table 16-2 Follow-up requirements for liver laboratory triggers - ALT, AST, TBL**

ALT or AST	TBL	Liver Symptoms	Action
ALT or AST increase without TBL increase:			
If normal at baseline: ALT or AST > 3.0 x ULN	Normal For participants with Gilbert's syndrome: No change in baseline TBL	None	
 
• No change to study treatment
 
• Measure ALT, AST, ALP, GGT, TBL, PT/INR, albumin, CK, and GLDH in 48-72 hours.
 
• Follow-up for symptoms.
 

If elevated at baseline: ALT or AST > 2 x baseline			
If normal at baseline: ALT or AST > 5.0 x ULN for more than two weeks	Normal For participants with Gilbert's syndrome: No change in baseline TBL	None	
 
• Interrupt study treatment
 
• Measure ALT, AST, ALP, GGT, TBL, PT/INR, albumin, CK, and GLDH in 48-72 hours.
 
• Follow-up for symptoms.
 
• Initiate close monitoring and workup for competing etiologies.
 

If elevated at baseline: ALT or AST > 3 x baseline for more than two weeks			
If normal at baseline: ALT or AST > 8.0 x ULN	Normal	None	
 
• Study treatment can be restarted only if another etiology is identified and liver enzymes return to baseline.
 
• If no cause can be identified to explain the elevation in liver enzymes, then study treatment must be discontinued.
 

ALT or AST increase with TBL increase:			
If normal at baseline: ALT or AST > 3.0 x ULN	TBL > 2.0 x ULN (or INR > 1.5) For participants with Gilbert's syndrome: Doubling of direct bilirubin	None	
If elevated at baseline: ALT or AST > 2 x baseline			
If normal at baseline: ALT or AST > 3.0 x ULN	Normal or elevated	Severe fatigue, nausea, vomiting, right upper quadrant pain	
If elevated at baseline: ALT or AST > 2 x baseline			

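### Section 9.1.1 makes eosinophilia a mandatory stop feature when ALT/AST exceed 3 x ULN, but no liver-trigger test list asks for the count and Table 16-2 gives a different feature list

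*Protocol*

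**What the plan says.** Protocol Section 9.1.1 lists the circumstances in which study treatment must be discontinued. The liver criteria share one opening condition: "Unexplained increases in transaminases (ALT or AST) or total bilirubin confirmed by repeat test as follows". One of them is ALT or AST above 3 x ULN with the appearance of any of a set of features, ending with "right upper quadrant pain or tenderness, fever, rash, and/or eosinophilia (> 5" (a percentage). The features are joined by and/or, so any one suffices.

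Eosinophils appear in one panel only, the Hematology row of Table 8-3: "Differential (% of Basophils, Eosinophils, Lymphocytes, Monocytes, Neutrophils". Table 8-1 schedules Hematology at Day 1 and Day 180.

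When a liver trigger is met, Section 10.2.1 asks sites to "Repeat liver chemistry tests (i.e., ALT, AST, TBL, albumin, CK, GLDH, PT/INR, ALP and GGT) to confirm elevation", and Table 16-2 to "Measure ALT, AST, ALP, GGT, TBL, PT/INR, albumin, CK, and GLDH in 48-72 hours". Table 16-2 describes the symptomatic case as "Severe fatigue, nausea, vomiting, right upper quadrant pain". For ALT/AST above 3 x ULN with normal bilirubin and no symptoms, its action is "No change to study treatment". Section 10.2.1 points back to the stop list with "Discontinuation of the investigational drug (refer to the Discontinuation of study treatment section), if appropriate", and Section 9.1.1 in turn refers the reader to Appendix 2.

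**The concern.** Eosinophilia is the only feature in this criterion that needs a laboratory test. It has a numeric cut-off, so neither questioning nor examination can replace the count. If the mandated tests do not produce the count, whether the criterion is checked depends on whether a site thinks of ordering it. Sites working from Table 16-2, the operational table, would also see a shorter feature list than the one that obliges them to stop.

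What is at stake is consistent protection of individual participants, not the efficacy analysis. The trial has no committees (Protocol Section 10.3), so site-level rules carry much of the safety oversight. The SAP names hepatotoxicity as an adverse event of special interest (SAP Section 2.7.1.1).

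**Working it through.** The plan gives no figure to reproduce. The check sets the schedule, the triggered tests and the stop list side by side.

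**Step 1. Scheduled samples (Table 8-1, panel content from Table 8-3).**

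| Visit | ALT/AST | Differential | Relation to dosing |
|---|---|---|---|
| Day 1 | yes | yes | before the first injection and capsule (Table 8-1 footnote 15; Section 6.3.2) |
| Day 30 | yes | no | on treatment |
| Day 90 | no | no | on treatment |
| Day 150 | yes | no | day after the last capsule |
| Day 180 | yes | yes | 180 − 149 = 31 days after the last capsule; 180 − 90 = 90 days after the last injection (nominal) |

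Scheduled eosinophil counts after the first dose and up to the last: 0. Day 30 is the only scheduled post-dose ALT/AST draw that comes before the last doses. Day 180 may be a telephone contact, in which case that sample is not taken either.

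**Step 2. Tests mandated after a liver trigger.**

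| List | Differential named? |
|---|---|
| Table 8-3, liver event and follow-up row | no (hemolysis tests are added, including reticulocytes) |
| Section 10.2.1 repeat | no |
| Table 16-2, 48-72 hour repeat | no |

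The drug-induced liver injury work-up in Section 6.6.3.1 does not name one either, but it applies only when bilirubin is also raised.

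**Step 3. Feature lists compared.**

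| Feature | Section 9.1.1 | Table 16-2 symptom cell |
|---|---|---|
| Fatigue | any | severe only |
| Nausea, vomiting | yes | yes |
| Right upper quadrant pain | yes | yes |
| Right upper quadrant tenderness | yes | no |
| Fever | yes | no |
| Rash | yes | no |
| Eosinophilia above 5% | yes | no |

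**Step 4. An illustrative case.** Take ALT of 4 x ULN at Day 30 with normal baseline enzymes, normal bilirubin and no symptoms.
- At the first result there is no conflict. Section 9.1.1 acts only after a repeat, and Table 16-2 keeps treatment unchanged and orders that repeat.
- Suppose the repeat confirms the rise and no cause is found. Section 10.2.1 then calls for close observation and for considering interruption.
- Section 9.1.1 requires a stop if eosinophilia above 5% has appeared, but none of the mandated lists has asked for the count.
- The participant still matches the Table 16-2 row for no symptoms.

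**Step 5. How many participants.** The documents give no rates, so both shares below are assumptions. Randomized total: about 300 (Protocol Section 12.8.1). Unexplained ALT/AST above 3 x ULN is excluded at screening (criterion 9).

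Number affected = 300 × share above 3 x ULN at Day 30 × share of those confirmed, unexplained and with eosinophilia as the only added feature.

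| Share above 3 x ULN | Participants | × 5% | × 20% |
|---|---|---|---|
| 0.5% | 300 × 0.005 = 1.5 | 0.075 | 0.3 |
| 2% | 300 × 0.02 = 6 | 0.3 | 1.2 |

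Only the extreme corner exceeds one participant.

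**The case against.** The strongest reply is that nothing prevents a site from applying the rule. Section 14 provides for additional safety assessments case by case, Section 9.1.1 tells the investigator to look for other causes, and Section 10.2.1 leaves further work-up to discretion. An investigator reading a rule that names eosinophilia has the authority to order a differential. Section 9.1.1 also keeps its other liver criteria, its general safety ground and its ground for other laboratory abnormalities. All of this stands. It shows that the test is permitted; it does not make its use uniform across sites.

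Two stronger readings are tempting, and the documents do not support them.

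- A reader might infer that Table 16-2 tells sites to continue treatment in a case where Section 9.1.1 tells them to stop. The no-change row works mainly as the first-result step, since it orders the repeat. Once the rise is confirmed, Section 10.2.1 moves to close observation and consideration of interruption, and it refers to the stop list. What remains is a mismatch between two feature lists.
- A reader might measure the harm by the doses a missed stop would allow. That would overstate exposure to active drug. Capsules are placebo in the inclisiran and placebo arms, (150 + 75)/300 = 75% of participants. Injections are placebo in the ezetimibe and placebo arms, (75 + 75)/300 = 50%. The placebo arm, 75/300 = 25%, receives no active drug.

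**Conclusion.** The point holds as a minor one. A site that runs every mandated test, and no others, cannot evaluate one sufficient feature of a mandatory stop criterion, and the Table 16-2 symptom cell does not match that criterion. The textual gap is certain. Its practical effect is small: probably about zero to one participant under the assumed rates, which have no basis in the documents beyond the total of about 300. A site can still apply the criterion; it is simply not prompted to. Sample size, power, type I error control and the planned analyses are unaffected.

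**What to change.** 1. Add hematology with differential to the repeat draw when ALT/AST exceed 3 x ULN, in three places: the liver row of Table 8-3, the Section 10.2.1 repeat and the Table 16-2 48-72 hour list.
2. Replace the Table 16-2 symptom cell with the Section 9.1.1 feature list, or put a cross-reference to Section 9.1.1 there.

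Enzyme thresholds stay as they are. The Day 1 hematology serves as the baseline for judging whether eosinophilia is new. An edit to Section 6.6.3.1 is optional: that work-up needs raised bilirubin, and above 2 x ULN a separate Section 9.1.1 criterion already applies.

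Costs:
- About one extra tube per liver repeat, at a draw already required (1.5 to 6 participants at Day 30 under the assumption above).
- A laboratory-manual change and a protocol amendment with the approvals in Section 14.1.
- An occasional extra permanent stop. In Section 9.1.1 the word unexplained qualifies the enzyme or bilirubin rise, not the eosinophilia. Read literally, new allergic eosinophilia alongside an unexplained, confirmed rise above 3 x ULN would end both treatments. Each such stop is an intercurrent event. Under the Monotherapy Estimand later efficacy values would be imputed; under the Treatment-policy Estimand the values collected after the stop would be used.
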